A snorkel-like tube connected to the amplifier was adopted for transmitting the generated waves through a mouthpiece commonly used for pulmonary function tests (Figure 3). To ensure the produced air pressure waves are transmitted down the respiratory system, the opposite end of the mouthpiece was connected to a 5 cm H₂O/L/sec respiratory resistor (Model #7100R, Hans Rudolph, Inc., Shawnee, KS) throughout both the inspiration and expiration portions of the breathing cycle. Sampling bags used for aerosol sampling were 1-liter Tedlarbags (SKC Inc., Pittsburgh, PA) which had internal dimensions of 241 · 254mm² as a deflated bag, with a wall thickness of *50 lm and single polypropylene (hose/valve and septum) fittings.

Study Device:

High Frequency Oscillator (HFO): The device involves 1) A mouthpiece commonly used in performing pulmonary function tests, or delivering nebulized medications and 2) A High-Frequency Oscillator (HFO) that will be connected via a side port to the mouth piece. This device transmits high frequency square form audio waves through a mouthpiece or mask interface to airways. HFO device vibrates the airways thereby lifting micro molecules of airway linings in to aerosols. During quiet tidal breathing, these aerosols escape the lungs through exhaled breath. Exhaled breath passes through a special filter that traps these aerosols and micro molecules of airway linings.

[figure not shown]
Study Procedures and the Device Interaction:

FIGURE 4

Figure 4: The PIAPD experimental device utilizes high frequency audio waves to oscillate aerosols in airway linings and allow the to escape through exhaled breath

FIGURE 5

present in exhaled breath.

Figure 5: this High Frequency Oscillator (HFO) has been designed to filter ASL as well as microparticles present in exhaled breath.

The study involves subjects breathing through a mouthpiece. The mouthpiece may be connected to HFO, or R tube exhaled breath condensate (EBC) device, other forms of commercially available EBC devices that collects exhaled breath or to an Aerosol Particle Counter (APC). The study procedure causes no discomfort and requires minimal patient cooperation.

The exhalation port of the mouthpiece of HFO will have a special filter that traps aerosolized airway surface liquid (ASL) as well as microparticles

Statistical Analysis

We shall cross-tabulate the pre- and post-treatment spirometry measures for study condition and group. Significance for association will be obtained by repeated measures ANOVA. The false positive and false negative rates will be estimated by exact binomial confidence limits. This is a pilot study that is seeking a promising outcome as opposed to a definitive one. We shall consider the result as promising if (a) no false positives occur and (b) the false negative rate is below 50%.

Power/Sample Size: The study will have a goal to recruit 50 CF (10 inpatient and 40 outpatient) patients. Initial data analysis to be completed after the first 25 patients have completed each test condition.

Measurable outcomes and expected timeline: We expect the PIAPD is equal to standard airway clearance in CF patients. We expect PIAPD will decrease the sense of breathing effort and increase patient sense of efficacy.

Compliance/Accountability/Regulatory

Statement of Compliance

This study will be conducted in compliance with the protocol and will be generally consistent with current Good Clinical Practices (GCP), adopting the principles of the Declaration of Helsinki and all applicable regulatory requirements (ICH E6, 45CFR46, and FDA 21CFR sections 11, 50, 56, 312).

Prior to study initiation, the protocol and the informed consent documents will be reviewed and approved by UF's Institutional Review Board (IRB). Any amendments to the protocol or consent materials will be approved before they are implemented.

Adverse Event Reporting and Safety Monitoring

In the event of an adverse event the following definitions and processes will be used/followed:

Adverse Event Definitions

In this clinical research study, an adverse event (AE) is any occurrence or worsening of an undesirable or unintended sign, symptom or disease that is associated with study procedures. As an observational study, AEs occurring between study visits will not be reported unless deemed associated with study procedures. Throughout the study, the investigator must record AEs related to study procedures on source documents regardless of severity.

Unexpected Adverse Event

An AE is considered unexpected when the nature (specificity) or severity of the event is not consistent with the risks described in the protocol or informed consent document for specific protocol-required interventions.

Grading Adverse Event Severity

This study will utilize the National Cancer Institute (NCI) Common Toxicity Criteria for Adverse Events (CTCAE Version 3.0) to classify AE severity.

All AEs Grade 2 or greater pertaining to study procedures will be recorded on the UF IRB adverse event log, which will be reviewed by the IRB annually at continuing review. The investigator will make a determination as to the relation to participation in the study. Events will be assessed and reported in accordance with the ICH Guidelines for Good Clinical Practice and per the guidance of the DHHS Office for Human Research Protections (OHRP). Should there be an adverse event or unanticipated problem that is both serious and unexpected it will be evaluated by the PI and reported to the IRB as appropriate per current regulatory guidelines.

Informed Consent

Participants will sign their own informed consent form (or in the case of parents, they will consent for their child). This study will require written assent from minors. This study does not allow for use of legally authorized representatives or LARs. Each participant will receive a signed copy of their informed consent for their records. Participants will have the opportunity to ask questions before they sign the consent form and when a study coordinator calls them to confirm their information.

Risks and Benefits

Aside from the normal shortness of breath, which is expected as part of doing standard of care airway clearance and pulmonary function testing, there are no discomforts or risks associated with study that we know of. This research study may also include risks that are unknown at this time. If the portable airway device works as well as the standard airway clearance device, it will potentially provide a less expensive, portable alternative for patients with CF that they can use in their homes without coming to clinic and during telemedicine visits with their physician.

It is also possible, that patients may not see an improvement and may even see a worsening of their airway clearance as measured by FEV-1 while using the experimental device.

Confidentiality

Investigators and staff will maintain the highest degree of confidentiality permitted for the clinical and research information obtained from subjects participating in this study. When a participant signs a consent they will be assigned a study ID which will be attached to their surveys and data. All study records will be locked in secure filing cabinets in locked offices in UF research space.

Conflicts of Interest

The investigators have no financial interests in any entity which could potentially benefit from the outcomes of this research. This study is internally funded by the Department of Medicine and the investigational device being used was created by [name] who has previously used the device in several UF IRB approved research protocols. This device has been reviewed by the UF Office of Technology and Licensing, who determined that the invention was not eligible for a patent or other licensing as it was too “similar” to currently approved/marketed products. The justification for the use of this device in the clinical space, is that it is much cheaper than the current airway clearance devices currently on the market making it ideal for patients with no insurance or lower incomes. Additionally, with the advent of COVID-19 patients with CF are at increased risk when leaving their house and coming to the clinic in order to perform pulmonary function testing and airway clearance. The device under investigation is portable and can be utilized in the home environment and monitored by the provider with telemedicine.

Protocol deviations

Any deviations from the protocol will be filed, as appropriate, on our deviation log and reported at the annual continuing review. Any deviations which have the potential to impact participant safety will be reported per UF guidelines.

Data handling and record keeping

Data collection will comply with all applicable guidelines regarding patient confidentiality and data integrity. REDCap data security protocols provide private, secure, and encrypted transmission of data between server and client computers over the public Internet network. All data systems are HIPAA compliant.

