Project Title: Airway Clearance for Pediatric and Adult Cystic Fibrosis Patients Using a Portable Intra-Pulmonary Percussion Device

Investigator(s): [name], [name], [name], [name], [name].

Abstract:

Airway clearance has a crucial role in the prevention of progression of lung disease in cystic fibrosis patients. Despite multiple options available for airway clearance, frequently cystic fibrosis patients have difficulties performing regular airway clearance in an at-home environment. We will compare pulmonary function testing and patient satisfaction with their current home device compared to the portable internal airway percussion device proposed (PIAPD). Our hypothesis is that there is no difference in pulmonary function testing after using PIAPD comparing to their home device. Our goal is to provide an equally effective, less expensive, alternative airway clearance technique for cystic fibrosis patients.

Background:

Cystic Fibrosis (CF) is an autosomal recessive disease that affects more than 30,000 people in the United States and more than 70,000 worldwide. The abnormal Cystic Fibrosis Transmembrane conductance regulator (CFTR) function leads to multiple organ manifestations. In the lungs, the dysfunctional CFTR mutation leads to abnormal thick, sticky mucus in the airways that traps microorganisms, leading to infections, inflammation and respiratory failure, which are the main causes of death in CF patients. Daily airway clearance plays a key role in preventing lung function deterioration in CF. Typically, a CF patient gets airway clearance therapy at least two times daily, each session lasting for about 30 minutes. There are different types of airway clearance therapies. Some of them are active, requiring patient cooperation and some coordination of breathing, while others are predominantly passive. In the United States, the most commonly utilized technique is high frequency chest wall oscillation, more commonly known as “the VEST”. This vibration loosens secretions in the bronchi that the patient will have to actively expel. The apparatus of vest therapy involves a wearable jacket, a hose pipe and an air compressor. This apparatus requires electric supply from the mains and is not portable.

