The PIAP device,(as pictured in Figure 4) that we have developed has been previously tested in several IRB-02 approved pilot studies here at the University of Florida by [name] in a population of healthy volunteers. Published results of these studies report this device's waves produce vibrations within the airways, loosening Airway Surface Liquid (ASL), enhancing airway clearance and decreasing the sense of breathing effort. Furthermore, the IAP device was found to painlessly increase exhalation of intra airway molecules and droplets in healthy individuals.

For this study, we would like to test this unique, custom designed, inexpensive, portable IAP device (PIAPD) as a comfortable alternative for airway clearance in CF patients.

Specific Aims:

1. To determine if Portable Internal Airway Percussion Device (PIAPD) is a non-inferior at-home method of airway clearance in patients with CF, we will compare changes in pulse oximetry and forced expiratory volume in one second (FEV1) prior to and 2 hours after airway clearance performed with standard airway clearance devices vs. the PIAPD. The primary endpoint will be a comparison of results of the aforementioned pulmonary function testing between the two devices.
2. Secondary endpoints include will include comparison of patient satisfaction (tolerability and acceptability) with standard airway clearance devices and PIAPD.
3. We will measure CF patient perception of breathing effort and device use for both methods.

Study Design: This is a pilot study where we aim to compare initial use of the standard airway clearance device (SACD) (as pictured in Figure 2) with subsequent use of a PIAPD in patients ages 6-21 years with stable CF. Our primary hypothesis, stated as Null, is that there is no effect of on FEV1 2 hours after use and there is no effect on perception of effort and efficacy for the PIAPD device.

General Inclusion Criteria:

- Ages 6-21 years
- Stable CF as determined by pulmonary physician assessment
- Assents to forego additional experimental treatments during the study
- Currently using and familiar with airway clearance therapy for treatment of CF
- Participant (or parent or legal guardian if the participant is a minor) is willing to provide Informed Consent

General Exclusion Criteria:

- FEV1 < 40% predictive
- Pneumothorax
- Hemoptysis

- COVID-19 diagnosis within last 14 days
- Non-compliance
- Inability to obtain informed consent

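### Aim 1 asks for non-inferiority, but the only spirometry test is ANOVA significance with no margin or interval, so a non-significant result or a significant deficit cannot settle it

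*Combined protocol and SAP*

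**What the plan says.** Specific Aims, aim 1, sets the question: "To determine if Portable Internal Airway Percussion Device (PIAPD) is a non-inferior at-home method of airway clearance in patients with CF". The comparison is of change in FEV1 and pulse oximetry from before to 2 hours after airway clearance, between the two devices.

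The hypotheses take another form. The Abstract says: "Our hypothesis is that there is no difference in pulmonary function testing after using PIAPD comparing to their home device". Study Design states a null that "there is no effect of on FEV1 2 hours after use" (the wording is garbled in the source). Neither is a non-inferiority null.

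Statistical Analysis has a descriptive cross-tabulation of spirometry and then one inferential sentence: "Significance for association will be obtained by repeated measures ANOVA". The only confidence limits are for something else: "The false positive and false negative rates will be estimated by exact binomial confidence limits". The decision rule rests on those rates: "We shall consider the result as promising if (a) no false positives occur and (b) the false negative rate is below 50" per cent.

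Power/Sample Size gives a goal of 50 patients (40 outpatient, 10 inpatient) with no alpha, SD, margin or power, and adds: "Initial data analysis to be completed after the first 25 patients have completed each test condition". The expected-outcomes paragraph says: "We expect the PIAPD is equal to standard airway clearance in CF patients".

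**The concern.** A non-inferiority question asks how much worse than the comparator the new device could still be, and whether that is tolerable. Answering it takes an interval for the difference and a limit to hold it against. The plan specifies neither. A test of no difference answers another question, and non-significance may reflect similar devices or an imprecise comparison.

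The 'promising' rule does not fill the gap. False positives and false negatives need a reference classification, and none is defined for comparing two devices on a continuous FEV1 change. The rule cannot be applied to Aim 1 as written.

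At stake is the trial's main conclusion. The Background builds the device's advantages in cost and portability on its being non-inferior, yet most results the stated analysis could give would leave that open.

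**Working it through.** **Is there a margin or interval anywhere?** The possible candidates are the 10% FEV1 figures. They appear in the additional exclusion criteria (outpatient decline over 12 months; inpatient failure to improve by day 9), in the choice of device on inpatient days 10-14, and in the stopping criteria under Safety Endpoints. All are thresholds for an individual patient. None limits a mean device difference. The figure of 50 patients cannot be reproduced, because no inputs are given for it.

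**What each ANOVA outcome would tell Aim 1.**
- Device effect not significant: neither non-inferiority nor equality is established.
- Significant PIAPD deficit: exact equality is refuted, but non-inferiority cannot be judged without a margin.
- Significant result favouring PIAPD: supports non-inferiority at any margin.

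**Illustration of scale.** From the documents: 40 outpatients in a two-period crossover, and an initial analysis at 25 patients. Assumed, because the documents give no values: SD of the within-patient device difference (s) of 5, 8, 10 or 12 FEV1 points, two-sided 5% level, true PIAPD deficit of 5 points. The device contrast is approximated by a paired t-test. The low SD allows for averaging: a one-session SD of 10 becomes 10/√4 = 5 over four sessions per device if all variation is between sessions.

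Formulas:
- Half-width of the 95% CI = t(0.975, n−1) × s/√n. For n = 40, 2.023/√40 = 0.320, so the half-width is 0.320 × s.
- Chance of non-significance = probability that a noncentral t with n−1 df and noncentrality 5/(s/√n) lies within ±t(0.975, n−1). For n = 40 and s = 10, the noncentrality is 5/1.581 = 3.16, giving 0.131.
- If the first 25 patients follow the planned 40:10 mix, outpatients number 25 × 40/50 = 20.

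| Assumed SD | 5 | 8 | 10 | 12 |
|---|---|---|---|---|
| Non-significant, 40 outpatients | <0.1% | 3% | 13% | 27% |
| Non-significant, 25 patients, all outpatients | 0.2% | 15% | 33% | 48% |
| Non-significant, about 20 outpatients among the 25 | 1% | 24% | 44% | 58% |
| 95% CI half-width, n = 40 | 1.6 | 2.6 | 3.2 | 3.8 |
| Lower limit of a just non-significant deficit, n = 40 (−2 × half-width) | −3.2 | −5.1 | −6.4 | −7.7 |

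**The other direction.** With n = 40 and SD 5, an observed difference of −2.0 has a 95% CI of −2.0 ± 1.6, that is −3.6 to −0.4. It is significant, yet lies wholly above an illustrative limit of −5.

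**Two looks.** If a claim based on the lower 95% limit were allowed at both 25 and 40 pairs, the correlation of the two statistics would be √(25/40) = 0.79. By normal approximation, the chance of at least one crossing of 1.96 is about 3.9%, against a nominal one-sided 2.5%.

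**The case against.** The strongest reply is that this is a pilot, which Statistical Analysis says seeks a promising rather than a definitive outcome. That stands as a reason to accept less certainty. It does not make a difference test into a non-inferiority test, and the pilot's own criterion is undefined for FEV1.

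A second reply is that a repeated-measures ANOVA fit yields a mean difference and error variance, from which an interval follows. That is true: the data and perhaps the model are adequate. What is missing is a commitment to report the interval, and a margin if non-inferiority is to be claimed.

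Third, all SDs and margins above are assumed, and at SD 5 with 40 pairs the risk of missing a 5-point deficit almost vanishes. That also stands. The figures show how the problem scales; they do not measure an error in this trial.

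Three stronger readings are tempting. A reader might infer that the ANOVA can say nothing about Aim 1 at any sample size. That goes too far: a significant result favouring PIAPD would support non-inferiority, and the Background regards superiority as possible in theory. A reader might infer that the investigators will read non-significance as equality. No sentence says so, and the remark about being equal is an expectation, not a decision rule. A reader might also infer that 40 outpatients are too few. Without an SD and a margin, that cannot be determined.

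**Conclusion.** The point holds in this form: Aim 1 is a non-inferiority question, and the plan's only inferential spirometry analysis can inform it in just one case, a significant result in PIAPD's favour. This follows from the text and needs no assumed SD. It is a mismatch between the aim and the analysis, not merely an omitted detail, and should be settled before the 25-patient data are seen.

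The size is conditional. For a true 5-point deficit, the chance of a non-significant result in 40 outpatients runs from under 0.1% to 27% over the assumed SDs. At the 25-patient analysis it runs from 0.2% to 48% if all 25 are outpatients, or from about 1% to 58% if about 20 are.

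**What to change.** In Statistical Analysis, make the primary result the mean within-patient PIAPD-minus-SACD difference in pre-to-2-hour FEV1 change, with a two-sided 95% CI.

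1. Name one FEV1 scale; percent predicted is already used for eligibility.
2. Use a crossover model with device, period and sequence terms and patient as a random effect, in the 40 outpatients. Report the 10 inpatients (days 4 and 5) separately.
3. Report pulse oximetry change the same way, as a supporting result or a named co-primary, since Aim 1 includes it.
4. Reconcile Study Design, which describes SACD first and PIAPD afterwards, with the later text that assigns devices at random. The model separates device from period only if order is randomised.
5. State whether the twice-weekly outpatient post-tests are also at 2 hours, as Aim 1's general wording may intend. If not, use the day 1 session of each period.
6. Choose one route:
   - Estimation: reword Aim 1 as estimating the difference, drop non-inferiority and equality as conclusions, and delete the 'promising' rule or base it on this interval.
   - Non-inferiority: before the 25-patient analysis, fix and justify a margin M. Claim non-inferiority only if the lower 95% limit is above −M. State the power for that M and a stated SD.
7. Apply any claim rule only at the final analysis.

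The cost is wording and analysis, with no extra patients under the estimation route. The claim narrows to an estimate with a 95% CI of about ±1.6, 2.6, 3.2 or 3.8 points at the assumed SDs. Averaging all sessions would need a fixed 2-hour wait at the telemedicine tests.

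Keeping non-inferiority may cost more. If the devices are equal, power with 40 pairs at SD 5/8/10/12 is 96%/64%/46%/34% for an illustrative M of 3 points and >99%/97%/87%/73% for 5 points.

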For the next two weeks, airway clearance therapy, either performed with SACD method or PIAPD, will be performed by the patient daily (CF patients perform airway clearance daily as part of standard of care for their disease). Spirometry/pulmonary function testing will be collected twice per week over the two-week period with a pre and post FEV1, pulse oximetry, and rating of breathing effort. This testing will be done via telemedicine so that the PI or co-investigator can assist the patient with the PIAPD if necessary and conduct the testing in a safe and efficacious manner. At the end of the two weeks, the participant will be asked to complete a short survey regarding the ease of use and acceptability of the airway clearance device they had been using for the first part of the study.

At the end of the initial 2-week period, the patient will be crossed-over to the other arm of the study and the same procedures will be repeated as per the above procedures. At the end of the study, patients will return the PIAPD device to the study team.

FIGURE 1

Figure 1: Smart One® portable home spirometer is the standard of care for at-home measurement of FEV-1.

Inpatient arm:

Patients who are admitted to the hospital for a normal seasonal disturbance of their CF are admitted, as SOC, for a 14-day in-patient stay. When patients are admitted, they bring their VEST system, as this is the standard of care device used by over 95% of CF patients for airway clearance therapy. Following admission, patients will be informed of the study by the PI or one of the designated co-investigators. All study procedures will be explained and ample time to ask questions will be allotted. If the patient agrees to participate written informed consent will be obtained and the following procedures performed:

Hospital Stay Days 1-3: Patients will only use their SOC airway clearance therapy. This will allow for a “wash-out period” providing all the patients with good airway clearance prior to collecting data (some patients may have had poor compliance prior to hospitalization). The participant will also be asked to complete a short survey regarding the ease of use and acceptability of their SOC airway clearance device, at the end of this 3-day wash-out period. Furthermore, during this period, we will get daily spirometry with a portable spirometer once per day after first airway clearance of the day, along with pulse oximetry.

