Hospital Stay Day 4: If, in the judgement of the PI, the participant has stabilized, we will randomize them to use either their SOC device or the study device. On Day 4, patients will be randomized to SOC or the new airway clearance device. We will collect the patient’s ratings of breathlessness with the Modified Borg Dyspnea Scale and perform spirometry again with the Smart One® portable spirometry device before and two hours after airway clearance procedures for the first airway clearance of the day. We will also obtain pulse oximetry.

Hospital Stay Day 5: we will alternate the modality for the first airway clearance session of the day (using whichever device they were not randomized to use on Day 4), repeating the Modified Borg Dyspnea Scale and performing spirometry again before and two hours after airway clearance along with pulse oximetry. At this point, they will have used both the airway clearance devices, and they will be asked to complete a short survey regarding the ease of use and acceptability of the study airway clearance device.

Hospital Stay Days 6-9: we will continue with daily spirometry, dyspnea measurements and pulse oximetry once per day after the first airway clearance of the day using the study device.

Hospital Stay Days 10-14: patients who have increased their FEV1 by at least 10% from admission by day 9 of hospitalization and whose symptoms have clinically improved, will be given the choice of whether to use their SOC device or the experimental study device. Whichever device they choose, they will use for two airway clearance sessions, along with dyspnea measurements, and pulse oximetry on days 10-14 of hospitalization.

At the end of the two weeks, the participant will be asked to complete a short survey regarding the ease of use and acceptability of each airway clearance device they had been using for the study. At the end of the study, we will ask that the patient return the experimental device to the study team.

FIGURE 2

Figure 2: The Vest® Airway Clearance System is the standard of care for airway clearance in both adult and pediatric

Safety Endpoints:

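### The planned repeated measures ANOVA on pre- and post-session FEV1 makes no adjustment for the pre-session reading; a patient-level crossover ANCOVA would be more precise, by an amount that depends on a correlation the documents do not give

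*Combined protocol and SAP*

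**What the plan says.** Specific Aim 1 sets the primary comparison: "we will compare changes in pulse oximetry and forced expiratory volume in one second (FEV1) prior to and 2 hours after airway clearance", between the standard device (SACD) and the PIAPD. The Statistical Analysis section gives two sentences on how this is tested: "We shall cross-tabulate the pre- and post-treatment spirometry measures for study condition and group", then "Significance for association will be obtained by repeated measures ANOVA". It names no factors, tested term, covariate, period effect or handling of repeated sessions.

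Each patient uses both devices. For outpatients, after two weeks "the patient will be crossed-over to the other arm of the study and the same procedures will be repeated". For inpatients, one device is randomised on Day 4 and on Day 5 "we will alternate the modality for the first airway clearance session of the day".

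Pre-session FEV1 is already collected where it is needed. Outpatients have it on Day 1, and after that "Spirometry/pulmonary function testing will be collected twice per week over the two-week period with a pre and post FEV1". Inpatients have it on Days 4 and 5, with spirometry "before and two hours after airway clearance procedures for the first airway clearance of the day". Days 6-9 differ: "we will continue with daily spirometry, dyspnea measurements and pulse oximetry once per day after the first airway clearance of the day", so those days have no pre-session value.

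**The concern.** With two time points, the device-by-time interaction in a repeated measures ANOVA is algebraically a comparison of change scores. The Statistical Analysis section does not say which term is tested, so this is an inference. It is the natural one, because Specific Aim 1 asks about changes, and a device main effect would average pre and post readings and dilute a within-session effect.

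A change score subtracts the whole pre-session reading. That reading contains measurement error and other variation not shared with the post-session reading, so the best-fitting slope is generally below 1. Fixing it at 1 carries all of that noise into the comparison. At stake is the width of the interval for the device difference. This matters because Specific Aim 1 asks a non-inferiority question and the recruitment goal is 50.

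**Working it through.** **What can be reproduced.** The only stated figure is the recruitment goal, 10 inpatients + 40 outpatients = 50. No SD, correlation, alpha, power or margin is given, so the size of the gain has to be shown over an assumed range.

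**Large-sample gain.** For each patient let d_pre and d_post be the PIAPD-minus-SACD differences in pre- and post-session FEV1. Assume each has variance s², with correlation ρ.

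- Change score: Var(d_post − d_pre) = 2s²(1 − ρ).
- Adjusted for d_pre: s²(1 − ρ²).
- Ratio: (1 − ρ²) / [2(1 − ρ)] = (1 + ρ)/2, so the reduction is (1 − ρ)/2.

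The relevant ρ is within-patient, because the crossover has already removed stable differences between patients.

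**Cost of estimating the slope.** With a period term, the adjusted variance is multiplied by about 1 + 1/(n − 4): 1.028 at n = 40, 1.048 at n = 25 (the size of the initial analysis) and 1.167 at n = 10. The net reduction is 1 − [(1 + ρ)/2] × that factor.

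| ρ (assumed) | Large sample | n = 40 | n = 25 | n = 10 |
|---|---|---|---|---|
| 0.4 | 30% | 28% | 27% | 18% |
| 0.7 | 15% | 13% | 11% | 1% |
| 0.9 | 5% | 2% | under 1% | 11% loss |

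Simulated AB/BA crossovers agree: 29%, 12% and 2% at n = 40; 18%, 1% and a 14% loss at n = 10.

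**Several sessions per period.** Outpatients have about 4 to 5 pre/post pairs per device (Day 1 plus twice weekly for two weeks). Averaging them can raise ρ and shrink the gain. Suppose 20% of within-patient variance is at patient-by-period level, 20% at day level and 60% is reading error (assumption). For one session ρ = 0.40. For a mean of five, the variance is 0.2 + 0.8/5 = 0.36 and the covariance is 0.2 + 0.2/5 = 0.24, so ρ = 0.67 and the large-sample gain falls from 30% to 17%.

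**Why the level of the model matters.** Take error variance 1, period-level variance p, day-level variance d and five sessions per period. The change-score variance per patient is 2 × 2/5 = 0.80.

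A session-level model with only a patient random effect and one within-patient slope has slope b of about (5p + 9d)/(5p + 9d + 9). Its variance is 2{p(1 − b)² + [d(1 − b)² + 1 + b²]/5}. The patient-level model on period means has ρ = (p + d/5)/(p + d/5 + 1/5).

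| p, d (assumed) | b | Session-level variance | Against 0.80 | Patient-level ρ | Patient-level reduction, net at n = 40 |
|---|---|---|---|---|---|
| 0, 1 | 0.50 | 0.60 | 25% lower | 0.50 | 23% |
| 0.5, 0.5 | 0.44 | 0.86 | 7% higher | 0.75 | 10% |
| 1, 0 | 0.36 | 1.28 | 60% higher | 0.83 | 6% |

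In simulation the session-level model had a type I error of about 10% to 11% in the second row and 20% to 21% in the third, because it treats sessions within a period as independent. The patient-level model uses one difference per patient and avoids this.

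**The case against.** **The change score matches the stated endpoint and is unbiased.** Device order is randomised, so a chance low pre-session reading adds noise that averages out. A reader might infer that the planned analysis gives a false gain; the documents do not support that. The point is about efficiency only.

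**No stated decision depends on it.** This is a pilot. Its rule for a promising result uses false-positive and false-negative rates, not the ANOVA, and no margin or alpha is given. That stands, and it limits the urgency. It does not remove the value of a tighter interval from data already in hand.

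**The covariate may not be a clean baseline.** After the first session of a period, the pre-session reading follows use of the assigned device, and no outpatient washout is stated. Suppose a device shifts pre-session FEV1 by 0.3 with no within-session effect, with p = d = 0.5 as above. The change score estimates 0, the session-level model 0.3 × (1 − 0.44) = 0.17, and the patient-level model 0.3 × (1 − 0.75) = 0.075. So the recommended model reduces this problem but does not abolish it. This is the strongest objection, and it is why other results must be reported beside the ANCOVA.

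**Stronger readings to avoid.** One might infer a firm gain of 15% to 30%, or convert it into patients saved. Those figures need ρ between 0.7 and 0.4, which no document supports. One might also infer that enrolment is capped; Power/Sample Size states only a goal.

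**Conclusion.** The point holds as a conditional gain in precision. The plan specifies no adjustment for a reading it already collects, and the ANOVA term that answers Specific Aim 1 is a change-score comparison. Adjustment lowers the variance of the device difference by about (1 − ρ)/2 in large samples. At n = 40 the net figure is 28%, 13% or 2% for ρ of 0.4, 0.7 or 0.9. Under the three five-session scenarios above it is 6% to 23%. In the 10 inpatients alone it may be nothing or a small loss.

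This rests on an assumed ρ, equal pre and post variances, and reading the tested term as device by time. The change is worth making because it is cheap, but only at patient level: a session-level model without period and patient-by-period terms can do worse than the current plan.

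**What to change.** Replace the ANOVA sentence with wording such as: *For each patient, the PIAPD-minus-SACD difference in 2-hour post-session FEV1, averaged over the test sessions in each period, will be regressed on the matching difference in pre-session FEV1, with a term for period. The adjusted device difference and its 95% confidence interval will be reported.*

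- An equivalent mixed model needs period and patient-by-period terms and must separate session-level from period-level effects of the covariate.
- Apply it to outpatient test sessions and inpatient Days 4-5 only. If the two arms are pooled, let period and slope differ by arm, since outpatient values are means of several sessions and inpatient values are single readings.
- Report beside it the change-score result and an analysis of the first session of each period, where the pre-session value precedes any use of the device in that period. The first-session analysis is less precise, and its second-period reading still follows two weeks on the other device.
- Fix the wording before the initial analysis at 25 patients, so that the covariate is not chosen after seeing data.

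The cost is SAP wording and one degree of freedom for the slope, with no new data collection. The price in interpretation is that the adjusted and change-score results can differ if a device shifts later pre-session readings.
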